should be preferred for uncomplicated malignant left-sided large bowel obstruction in absence of other risk factors. Patients with high surgical risk are better managed with Hartmann's procedure

Despite the growing evidence in favour of primary anastomosis and its inclusion as a valid treatment option for perforated diverticulitis or perforated sigmoid colon in recent clinical practice guidelines, some surgeons have been hesitant to undertake anastomosis in the setting of purulent or faecal contamination and continue to choose Hartmann's procedure to eliminate concerns about anastomotic leakage.

Primary study objective:

GOODBYE HARTMANN – AFTER 100 YEARS HARTMANN'S PROCEDURE IS GOING TO BE ABANDONED?

STUDY PROTOCOL WITH ICF - VERSION 2 09.03.2021

1. To evaluate the role of Hartmann's procedure in emergency setting for left-sided colonic acute surgical disease (perforated diverticulitis with purulent or fecal peritonitis; colon cancer perforation-occlusion; ischemic colitis; abdominal trauma) and the type of surgery commonly performed in different level of care hospitals.
2. To investigate which factors contribute in the choice of Hartmann's procedure instead of colon resection with primary anastomosis (Hospital characteristics, surgeon experience, time of surgery, age of patients, comorbidities, etc)

Study design: International multicenter prospective cohort study.

Study population: Adult patients with left-sided colonic acute surgical disease who need surgery in an emergency setting (perforated diverticulitis with purulent or fecal peritonitis; colon cancer perforation-occlusion; ischemic colitis; abdominal trauma). All patients undergoing urgent surgery will be invited to participate and can choose to consent or decline

Primary outcome: Hartmann's procedure vs colonic resection with primary anastomosis performed in a 3-months interval in an emergency setting for left-sided acute surgical colonic diseases.

Secondary outcomes: risk factors for Hartmann procedure (Hospital characteristics (secondary, tertiary level, trauma center), surgeon experience, time of surgery (day of surgery- weekend; day or night), patient's age, comorbidities, clinical status etc.

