5.4 SAMPLE SIZE CALCULATION

The data will be used to investigate the specific characteristics to choose Hartmann's procedure versus primary anastomosis for left-sided acute surgical colonic diseases. Based on literature findings it has been estimated that, on average, three patients will undergo urgent left-sided colonic diseases resection per month at each participating centre. Applying root mean square percentage error (rMSPE) of 15%, 500 patients treated with left colon resection with or without primary anastomosis should be included.

Inclusion of 500 patients will be sufficient to analyze primary study objective 1 and primary study objective 2. Therefore, the aim is to include at least 500 patients.

METHODS

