6. ANALYSIS

6.1 ANALYSIS STRATEGY

The first study objective is to investigate what factors contribute in the choice of Hartmann's procedure instead of colonic resection with primary anastomosis and what type of surgery is commonly performed in different level of care hospitals

Univariate analysis is performed on relevant parameters that are described in chapter 5.7- list of study parameters and 5.8-patient characteristics. Factors that are considered to be clinically relevant based on literature and/or expert opinion are selected for multivariate analysis.

Backwards selection is used to exclude values of $p > 0.05$ from the model.

The results obtained by the described analyses will also be performed in subgroups of patients who underwent Hartmann's procedure or primary anastomosis with or without diverting ileostomy. By performing this sensitivity analysis, we will investigate the factors behind the choice to perform Hartmann's procedure or colic resection with primary anastomosis.

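### The backward-selection rule in section 6.1 leaves clinically chosen factors with p above 0.05 without an adjusted estimate, so the adjusted results for a primary objective are a significance-filtered set

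*Protocol*

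**What the plan says.** Protocol section 6.1 sets out three steps. First: "Univariate analysis is performed on relevant parameters that are described in chapter" 5.7 (study parameters) and 5.8 (patient characteristics). Second: "Factors that are considered to be clinically relevant based on literature and/or expert opinion are selected for multivariate analysis". Third: "Backwards selection is used to exclude values of" p above 0.05 from the model.

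No other multivariate model is described. The analysis that 6.1 calls a sensitivity analysis repeats the same analyses in treatment subgroups, so it carries the same rule.

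The model serves an explanatory aim. The second primary objective in the Summary begins "To investigate which factors contribute in the choice of" Hartmann's procedure over resection with primary anastomosis, and 6.1 itself opens with this aim as the first study objective. On size, section 5.4 states: "Inclusion of 500 patients will be sufficient to analyze primary study objective 1 and primary study objective 2".

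**The concern.** The second step is sound, because the factors enter on subject-matter grounds and not on a univariate p-value. The third step then makes the p-value decide which of them get an adjusted result.

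For an explanatory question, a factor with a wide interval around a modest odds ratio is a finding in itself: the data do not settle whether it matters. Once the factor is removed, that statement is gone. Only an unadjusted univariate figure remains, and it cannot stand in for the adjusted one when candidates are correlated, as age, Charlson index and ASA class plausibly are. A reader may well take removal to mean that the factor plays no part.

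The surviving odds ratios are also read as the study's answer, although they were picked because they reached significance.

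**Working it through.** **Inputs.** From the protocol: n = 500 (5.4), removal at p above 0.05 (6.1), and a binary outcome of Hartmann's procedure versus primary anastomosis (5.5). Logistic regression and a two-sided Wald test are assumed, since 6.1 names neither. The Hartmann share, factor prevalences, number of model terms, correlations and effect sizes are not given, so all of these are assumptions.

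**The plan's own figure.** The 500 cannot be rebuilt from the stated 15% rMSPE, because neither the outcome share nor the number of predictors is given. It is used here only as the size of the model.

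**Hand check, one binary factor.** Take prevalence 0.3, Hartmann share 0.5 and a true odds ratio of 1.5.

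- SE of the log odds ratio = √[1/(500 × 0.5 × 0.5 × 0.3 × 0.7)] = √(1/26.25) = 0.195.
- ln 1.5 = 0.405, and the significance limit is 1.96 × 0.195 = 0.383.
- Probability of being kept ≈ Φ[(0.405 − 0.383)/0.195] ≈ 0.55.
- Mean odds ratio when kept (truncated normal) = 1.73, with log 0.548.
- Mean log odds ratio when dropped = (0.405 − 0.55 × 0.548)/0.45 ≈ 0.23, an odds ratio of about 1.26.
- Interval around it: exp(0.23 ± 0.383) ≈ 0.86 to 1.85.

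For a true odds ratio of 1.3 the same formulas give kept 0.27 and a mean of 1.65 when kept. For 2.0 they give 0.94 and 2.05.

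**Simulation.** n = 500, 10 to 25 binary factors at 30% prevalence, latent correlation 0 or 0.2, Hartmann share one third to two thirds. Factors are eliminated one at a time at p above 0.05, and means are geometric.

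| True OR | Kept | Mean OR when kept | Full model, mean over all runs | Full model, significant |
|---|---|---|---|---|
| 1.3 | 24–28% | 1.69–1.85 | 1.31–1.32 | 20–26% |
| 1.5 | 47–53% | 1.76–1.93 | 1.52–1.55 | 40–53% |
| 2.0 | 88–94% | 2.07–2.25 | 2.03–2.10 | 83–93% |

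With 15 factors and a Hartmann share of about one half, nominal 95% intervals for kept factors at a true 1.3 cover the truth in about 85–89% of cases, against 94–95% for the full model over all runs.

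**What is lost on dropping.** Where a true 1.5 is dropped, the full model would have shown about 1.26–1.28. Its typical interval runs from about 0.8 to 1.9–2.0 and contains 1.5 in 94–96% of cases.

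**Where the excess comes from.** The means when kept should not be set only against the full-model means over all runs. For the same kept factors in the same datasets (15 factors, correlation 0 and 0.2):

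- True 1.3: backward selection 1.70–1.74, full model about 1.71.
- True 1.5: backward selection 1.77–1.81, full model 1.78–1.79.

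The backward step itself adds nothing at correlation 0, about 0.03 at 0.2 and about 0.1 at 0.5. The rest is the effect of looking only at significant results.

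**Sensitivity at a true 1.5.** Prevalence 15%: kept 39%, mean 2.10. Prevalence 50%: kept 61%, mean 1.75. A continuous factor with 1.5 per SD: kept 98%, mean 1.55. At n = 1200: kept 80–88%, mean 1.55–1.61.

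**The case against.** The strongest objection is that backward selection does not cause most of the inflation. In a given study a full model would print nearly the same odds ratio for a factor that was kept. This stands. A reader might infer from the table that the backward step turns a true 1.3 into 1.7, and that a full model would cure it. It would not, for any reader who looks only at its significant rows. The benefit comes from reporting every row.

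A reader might also infer that the rule makes the study miss factors that a full model would find. That is not supported either. Low retention reflects limited power at about 500 patients, and with correlated factors the full model flags slightly fewer true ones.

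It can be said that the starting model might be tabulated anyway, perhaps under an analysis plan that is not shown. Section 6.1 does not exclude this, but it does not provide for it, and the rule with its threshold is fixed in the protocol. The point concerns that stated rule, not a missing detail.

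Three further limits are fair. The Summary also lists risk factors for Hartmann's procedure under secondary outcomes, although it makes the contributing factors a primary objective. Many candidates in 5.7 and 5.8 are multi-category, which was not simulated, or continuous, where strong effects are hardly touched. And 500 is a floor ("the aim is to include at least 500 patients"), so the harm shrinks if more are enrolled.

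**Conclusion.** The point holds as one of selective reporting and should be fixed. The main harm is that clinically chosen factors which miss p = 0.05 have no adjusted odds ratio or interval. For a binary factor with a true odds ratio of 1.5, that happens in roughly half of studies of this size. The secondary harm is that the adjusted odds ratios left in the model overstate weak-to-moderate binary effects on average, mostly because only significant ones are shown.

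The figures rest entirely on assumed effect sizes, prevalences, correlations, number of terms and Hartmann share, so they indicate scale and do not predict this study's results. The direction does not depend on the particular values chosen. Effects of 2 or more and strong continuous factors are little affected. The count of Hartmann's procedures versus primary anastomoses in 5.5 is not affected at all.

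**What to change.** In section 6.1, replace the sentence on backwards selection with:

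> The factors selected on literature and expert opinion are listed before analysis and all kept in the multivariate model; every factor is reported with its adjusted odds ratio and 95% confidence interval whatever its p-value. Any backward-selected model is secondary.

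This needs no new data and no more patients. It costs a longer reported model and a factor list that must be agreed, and kept to a workable length for about 500 patients, before analysis. It will not raise the number of significant factors.

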7. ETHICS STATEMENT AND REGULATORY APPROVAL

This study will be conducted in compliance with the principles of the declaration of Helsinki. The study protocol and relevant documents have been approved by the medical ethical committee of the Parma University Hospital. All participating centers are provided with the study protocol and

GOODBYE HARTMANN – AFTER 100 YEARS HARTMANN'S PROCEDURE IS GOING TO BE ABANDONED?

STUDY PROTOCOL WITH ICF - VERSION 2 09.03.2021

relevant documents in March 2021, so that participating centers can ask their local ethical committees for approval if needed according to local ethical protocols.

8. DATA HANDLING

8.1 DATABASE SYSTEM

Data will be collected and stored online through a secure server running the Research Electronic Data Capture (REDCap) web application. REDCap allows collaborators to enter and store data in a secure system. A designated collaborator at each participating site will be provided with REDCap project server login details, allowing them to securely submit data on to the REDCap system. REDCap has previously been successfully used for a range of other international cohort studies led by the central unit.

8.2 CASE REPORT FORM (CRF)

A detailed CRF is created from REDCap database and provided to the invited centers (see also appendix 1). The CRF includes info points with definitions and guidelines that aid in adequate scoring of the listed parameters.

8.3 DATA COLLECTION AND DATA ENTERING

All patient data will be entered anonymously by or under supervision of the treating physician(s). Only anonymised data will be uploaded to the database. No patient identifiable data will be collected. Data collected will be on comorbidities, treatment/operation. No dates (e.g. date of surgery) will be collected. The study will be carried out in accordance with national and international guidelines, as well as the basic principles of the protection of the rights and dignity of Human Beings, as set out in the Helsinki Declaration (64th Assembly Fortaleza, Brazil, in October 2013), and according to current legislation.

8.4 DATA PRIVACY STATEMENT

All anonymous study data will be available to the GOODBYE HARTMANN study team. The data of a center will be available to that specific center only through the REDCAP database system website. The data will not contain identifiable patient parameters (e.g. no date of birth etc.) in compliance with the General Data Protection Regulation (GDPR - EU 2016/679). Each patient will be coded with a unique patient number so that patients in the study are untraceable from the study database. Surgeons that participate in the GOODBYE HARTMANN study are asked to keep a password coded file that can identify individual patients locked away in their practice.

GOODBYE HARTMANN – AFTER 100 YEARS HARTMANN'S PROCEDURE IS GOING TO BE ABANDONED?
STUDY PROTOCOL WITH ICF - VERSION 2 09.03.2021

9. PUBLICATIONS

The GOODBYE HARTMANN study embraces cooperative authorship and all collaborators that contribute to this study will form the GOODBYE HARTMANN collaborative group. Every This group will co-author all publications in which GOODBYE HARTMANN study data is used.

The protocol writing committee is fully involved in conducting this study and will be included as authors in both main publications in which the GOODBYE HARTMANN study data is used. If the manuscript is submitted to a journal that does not allow the full number of authors, a number of authors will join the collaborative group instead, based on scientific input during the study, manuscript writing and revising.

